### 6.5.7 Physical examinations

The number and percent of patients with physical examination abnormalities will be summarized based on the safety analysis set for each treatment group and overall. Physical examination findings will be presented in a data listing.

No subgroup analyses will be performed.

## 7. Document history and changes in the planned statistical analysis:

Abbreviated SAP Version 1.0 dated 14 MAY 2015

Abbreviated SAP Version 2.1 dated 22 JUN 2017

SAP Version 3.0 dated 12 MAR 2018

SAP Version 4.0 dated 10 AUG 2018

SAP Version 4.1 dated 13 SEP 2018

## 9. Appendices

### 9.1 Study event schedule

Study event schedule during the double-blind study treatment period

Protocol activities	Screening period	Study treatment period (Darolutamide (ODM-201) or placebo)				End-of-study treatment visit
		Visit 1	Visit 2	Visit 3	Visit 4 and subsequent visits	
	Within 28 days before randomization	Day 1 	Day 15 (±3 days)	Day 29 (±5 days)	Week 16 (±7 days) and every subsequent 16 weeks	28 days (+7 days) after last dose
FACT-P or PCS of FACT-P	x (FACT-P)	x (FACT-P)			x 	x (FACT-P)
EQ-5D-3L	x	x			x 	x 
Physical examination, weight	x 	x		x	x	x
12-lead ECG and vital signs	x 	x 	x	x	x	x
Laboratory safety assessments	x	x	x	x	x	x
Serum PSA 	x	x			x	x
Testosterone	x	x			x	
PK samples at participating centres 			x	x	x	

Protocol activities	Screening period	Study treatment period (Darolutamide (ODM-201) or placebo)				End-of-study treatment visit
		Visit 1	Visit 2	Visit 3	Visit 4 and subsequent visits	
PK diary dispensing 		x	x	x		
PK diary collection 			x	x	x	
ECOG performance status	x				x	x
Pain diary dispensing	x			x	x	x
Pain diary collection 		x			x	x
Chest, abdomen and pelvic CT/MRI	x 				x 	
Bone scan 	x 				x 	
First SSE			x	x	x	x
First prostate cancer-related invasive procedure			x	x	x	x
Survival status			x	x	x	x
Adverse events 	x	x	x	x	x	x
Concomitant treatments 	x	x	x	x	x	x
Study drug dispensing and accountability		x		x	x	x 

Protocol activities	Screening period	Study treatment period (Darolutamide (ODM-201) or placebo)				End-of-study treatment visit
		Visit 1	Visit 2	Visit 3	Visit 4 and subsequent visits	
PG IC	x 					
PG sample		x 				
Tumor-related biomarker blood sample 		x				x

Abbreviations: IC = informed consent; ECG = electrocardiogram; ECOG = Eastern Cooperative Oncology Group; PG = pharmacogenomics; HR = heart rate; PK = pharmacokinetic; PSA = prostate-specific antigen; SSE = symptomatic skeletal event

-  In case the start of study treatment is not logistically feasible on the same day as randomization can be performed 1 day before the initiation of study treatment.
-  FACT-P (Appendix 5a) will be assessed at the week 16 visit only, and PCS subscale of FACT-P (Appendix 5b) will be assessed at the subsequent 16-week visits thereafter.
-  EQ-5D-3L (Appendix 6) will be assessed at the week 16 visit only, and end-of-study treatment visit.
-  Also height will be recorded at the screening visit.
-  A triplicate 12-lead ECG including HR in a supine position after at least 10 minutes rest. The 3 consecutive recordings will be performed within approximately 5 minutes. BP and HR (unless recorded by ECG) in a supine position after at least 10 minutes rest. The assessments will be done in the following order: ECGs, vital signs, and any type of blood draw as the last assessment.
-  See Section 6.2 for PK procedures (blood sampling and recording of 12-lead ECG and vital signs) at study centers participating in PK sample collection. If PK sampling is not feasible during these visits, later visits may be used for PK procedures.
-  Patients will be instructed to complete the diary for 6 days (-6 to -1 day) before day 1 and every 16-week visits until documented pain progression.
-  CT/MRI and bone scans are acceptable if performed within 42 days prior to start of study treatment. A local qualified site physician (e.g. site radiologist or PI, at the PI's discretion) must first review the screening scans and confirm the patient is non-metastatic before submitting the scans to central review to confirm eligibility. If the local qualified site physician detects metastasis, the scans should not be submitted to central review. For guidance on CT/MRI and bone scans performed at Week 16 and subsequent visits see Section 6.1.2.4.
-  New lesion(s) in bone scan must be confirmed by CT/MRI (whichever imaging was conducted at screening for soft tissue) or x-ray. If confirmatory scan is negative (does not confirm progression), the patient will continue study treatment and visit study center as specified in the study event table.

 All AEs including SAEs will be recorded from the date of signing IC and continuing until the end-of-study treatment visit. Any AEs or SAEs that occur after the end-of-study treatment visit and which are considered to be related to the study treatment or any study procedures have to be reported and entered into the eCRF. When the eCRF is not available anymore, all SAEs considered study treatment related should be reported to Bayer using a paper SAE form. AEs related to study procedures and all SAEs will be recorded for screening failures.

 Once the patient has been withdrawn from study treatment, concomitant treatments will be recorded if used to treat new related or unresolved related AEs or if it is an antineoplastic therapy.

 An optional PG IC for pharmacogenetics research study will be obtained at screening visit (or later during the study if feasible) unless precluded by local guidelines, e.g. IEC/IRB or regulatory authorities.

 Blood (plasma) sampling for tumor-related biomarker evaluation will be collected on day 1 visit before study treatment administration and at the end-of-study treatment visit unless precluded by local guidelines, e.g. IEC/IRB or regulatory authorities.

 The local PSA result taken at screening should be used to confirm the patient has CRPC (inclusion criterion 4) and meets inclusion criterion 6.

 Only study drug accountability performed at the end-of-study treatment visit.

 A blood sample for DNA extraction will be taken at day 1 visit (or later during the study if feasible) only from patients who have signed the PG IC unless precluded by local guidelines, e.g. IEC/IRB or regulatory authorities.

**Study event schedule during the follow-up period after withdrawal of study treatment**

Protocol activities	For patients during double-blind period before confirmed metastasis and not initiating any prohibited treatment	For patients after confirmed metastasis or for patients in the placebo arm at unblinding
	Visits Every 16 weeks ( $\pm 7$ days) from end-of-study treatment visit 	Visits or phone contacts Every 16 weeks ( $\pm 7$ days) from end-of-study treatment visit 
BPI-SF	X	X
Dispensing of pain diary	X	X
Collection of pain diary and pain medications	X 	X 
PCS subscale of FACT-P	X	X
ECOG performance status	X	X
Use of subsequent antineoplastic therapies	X	X
Collection of AEs and SAEs considered to be related to study treatment or procedures	X	X
Collection of concomitant treatments used to treat new related or unresolved related AEs	X	X
First SSE	X	X
First prostate cancer-related invasive procedure for prostate cancer	X	X

Protocol activities	For patients during double-blind period before confirmed metastasis and not initiating any prohibited treatment	For patients after confirmed metastasis or for patients in the placebo arm at unblinding
	Visits Every 16 weeks ( $\pm 7$ days) from end-of-study treatment visit 	Visits or phone contacts Every 16 weeks ( $\pm 7$ days) from end-of-study treatment visit 
Survival status	X	X
Serum PSA	X	
Chest, abdomen, and pelvic CT/MRI	X	
Bone scan 	X	

) Until confirmed metastasis, death or the end of the study

) Until death or the end of the study

) Patients will be instructed to complete the diary for 6 days before each 16-week visit until documented pain progression. Pain medications will be recorded on CRFs at each 16-week visit until documented pain progression.

) New lesion(s) in bone scan must be confirmed by CT/MRI (whichever imaging was conducted at screening for soft tissue) or x-ray. If confirmatory scan is negative (does not confirm progression), the patient will continue to visit study center as specified in the study event table.

7. What treatments or medications are you receiving for your pain?

---

---

8. In the last 24 hours, how much relief have pain treatments or medications provided? Please circle the one percentage that most shows how much relief you have received.

0% 10% 20% 30% 40% 50% 60% 70% 80% 90% 100%  
 No Complete  
 Relief Relief

9. Circle the one number that describes how, during the past 24 hours, pain has interfered with your:

**A. General Activity**

0 1 2 3 4 5 6 7 8 9 10  
 Does not Completely  
 Interfere Interferes

**B. Mood**

0 1 2 3 4 5 6 7 8 9 10  
 Does not Completely  
 Interfere Interferes

**C. Walking Ability**

0 1 2 3 4 5 6 7 8 9 10  
 Does not Completely  
 Interfere Interferes

**D. Normal Work (includes both work outside the home and housework)**

0 1 2 3 4 5 6 7 8 9 10  
 Does not Completely  
 Interfere Interferes

**E. Relations with other people**

0 1 2 3 4 5 6 7 8 9 10  
 Does not Completely  
 Interfere Interferes

**F. Sleep**

0 1 2 3 4 5 6 7 8 9 10  
 Does not Completely  
 Interfere Interferes

**G. Enjoyment of life**

0 1 2 3 4 5 6 7 8 9 10  
 Does not Completely  
 Interfere Interferes

Copyright 1991 [name]  
 Pain Research Group  
 All rights reserved.

**Scoring:**

Pain Severity Score = mean of items 3-6

(pain at its worst, pain at its least, pain on the average, pain for right now)

Pain Interference Score = mean of items 9A-9G (interference of pain with: general activity, mood, walking ability, normal work, relations with other people, sleep, and enjoyment of life).

**9.3 FACT-P questionnaire and scoring information**

PCS subscale of FACT-P concerns the “additional concerns” questions.

FACT-P (Version 4)

Below is a list of statements that other people with your illness have said are important. By circling one (1) number per line, please indicate how true each statement has been for you during the past 7 days.

PHYSICAL WELL-BEING		Not at all	A little bit	Some-what	Quite a bit	Very much
GP1	I have a lack of energy.....	0	1	2	3	4
GP2	I have nausea.....	0	1	2	3	4
GP3	Because of my physical condition, I have trouble meeting the needs of my family.....	0	1	2	3	4
GP4	I have pain.....	0	1	2	3	4
GP5	I am bothered by side effects of treatment.....	0	1	2	3	4
GP6	I feel ill.....	0	1	2	3	4
GP7	I am forced to spend time in bed .....	0	1	2	3	4
SOCIAL/FAMILY WELL-BEING		Not at all	A little bit	Some-what	Quite a bit	Very much
GS1	I feel close to my friends .....	0	1	2	3	4
GS2	I get emotional support from my family.....	0	1	2	3	4
GS3	I get support from my friends.....	0	1	2	3	4
GS4	My family has accepted my illness.....	0	1	2	3	4
GS5	I am satisfied with family communication about my illness .....	0	1	2	3	4
GS6	I feel close to my partner (or the person who is my main support).....	0	1	2	3	4
Q1	Regardless of your current level of sexual activity, please answer the following question. If you prefer not to answer it, please check this box  and go to the next section.					
GS7	I am satisfied with my sex life.....	0	1	2	3	4

FACT-P (Version 4)

By circling one (1) number per line, please indicate how true each statement has been for you during the past 7 days.

**EMOTIONAL WELL-BEING**

		Not at all	A little bit	Some-what	Quite a bit	Very much
GE1	I feel sad.....	0	1	2	3	4
GE2	I am satisfied with how I am coping with my illness .....	0	1	2	3	4
GE3	I am losing hope in the fight against my illness .....	0	1	2	3	4
GE4	I feel nervous .....	0	1	2	3	4
GE5	I worry about dying .....	0	1	2	3	4
GE6	I worry that my condition will get worse.....	0	1	2	3	4

**FUNCTIONAL WELL-BEING**

		Not at all	A little bit	Some-what	Quite a bit	Very much
GF1	I am able to work (include work at home).....	0	1	2	3	4
GF2	My work (include work at home) is fulfilling .....	0	1	2	3	4
GF3	I am able to enjoy life.....	0	1	2	3	4
GF4	I have accepted my illness .....	0	1	2	3	4
GF5	I am sleeping well.....	0	1	2	3	4
GF6	I am enjoying the things I usually do for fun.....	0	1	2	3	4
GF7	I am content with the quality of my life right now .....	0	1	2	3	4

FACT-P (Version 4)

By circling one (1) number per line, please indicate how true each statement has been for you during the past 7 days.

ADDITIONAL CONCERNS		Not at all	A little bit	Some- what	Quite a bit	Very much
C2	I am losing weight .....	0	1	2	3	4
C6	I have a good appetite.....	0	1	2	3	4
P1	I have aches and pains that bother me .....	0	1	2	3	4
P2	I have certain parts of my body where I experience significant pain.....	0	1	2	3	4
P3	My pain keeps me from doing things I want to do .....	0	1	2	3	4
P4	I am satisfied with my present comfort level.....	0	1	2	3	4
P5	I am able to feel like a man.....	0	1	2	3	4
P6	I have trouble moving my bowels .....	0	1	2	3	4
P7	I have difficulty urinating .....	0	1	2	3	4
BL2	I urinate more frequently than usual.....	0	1	2	3	4
P8	My problems with urinating limit my activities .....	0	1	2	3	4
BL5	I am able to have and maintain an erection .....	0	1	2	3	4

**FACT-P Scoring Guidelines (Version 4)**

Instructions:

1. Record answers in "item response" column. If missing, mark with an X
2. Perform reversals as indicated, and sum individual items to obtain a score.
3. Multiply the sum of the item scores by the number of items in the subscale, and then divide by the number of items answered. This produces the subscale score.
4. Add subscale scores to derive total scores (TOI, FACT-G & FACT-P).
5. The higher the score, the better the QOL.

Subscale	Item Code	Reverse item?	Item response	Item Score
PHYSICAL WELL-BEING (PWB)	GP1	4 -	_____	= _____
	GP2	4 -	_____	= _____
	GP3	4	_____	= _____
	GP4	4 -	_____	= _____
	GP5	4 -	_____	= _____
	GP6	4 -	_____	= _____
	GP7	4 -	_____	= _____
Score range: 0-28				

*Sum individual item scores: \_\_\_\_\_*

*Multiply by 7: \_\_\_\_\_*

*Divide by number of items answered: \_\_\_\_\_ =*

**PWB subscale score**

SOCIAL/FAMILY WELL-BEING (SWB)	GS1	0 +	_____	= _____
	GS2	0 +	_____	= _____
	GS3	0 +	_____	= _____
	GS4	0 +	_____	= _____
	GS5	0 +	_____	= _____
	GS6	0 +	_____	= _____
	GS7	0 +	_____	= _____
Score range: 0-28				

*Sum individual item scores: \_\_\_\_\_*

*Multiply by 7: \_\_\_\_\_*

*Divide by number of items answered: \_\_\_\_\_ =*

**SWB subscale score**

EMOTIONAL	GE1	4	-	_____	= _____
WELL-BEING	GE2	0	+	_____	= _____
(EWB)	GE3	4	-	_____	= _____
Score range: 0-24	GE4	4	-	_____	= _____
	GE5	4	-	_____	= _____
	GE6	4	-	_____	= _____

*Sum individual item scores:* \_\_\_\_\_

*Multiply by 6:* \_\_\_\_\_

*Divide by number of items answered:* \_\_\_\_\_ = **EWB subscale score**

FUNCTIONAL	GF1	0	+	_____	= _____
WELL-BEING	GF2	0	+	_____	= _____
(FWB)	GF3	0	+	_____	= _____
Score range: 0-28	GF4	0	+	_____	= _____
	GF5	0	+	_____	= _____
	GF6	0	+	_____	= _____
	GF7	0	+	_____	= _____

*Sum individual item scores:* \_\_\_\_\_

*Multiply by 7:* \_\_\_\_\_

*Divide by number of items answered:* \_\_\_\_\_ = **FWB subscale score**

**FACT-P Scoring Guidelines (Version 4) – Page 2**

Subscale	Item Code	Reverse item?		Item responds	Item Score
PROSTATE	C2	4	-	_____	= _____
CANCER	C6	0	+	_____	= _____
SUBSCALE	P1	4	-	_____	= _____
(PCS)	P2	4	-	_____	= _____
Score range: 0-48	P3	4	-	_____	= _____
	P4	0	+	_____	= _____
	P5	0	+	_____	= _____
	P6	4	-	_____	= _____
	P7	4	-	_____	= _____
	BL2	4	-	_____	= _____
	P8	4	-	_____	= _____
	BL5	0	+	_____	= _____

**Sum individual item scores:** \_\_\_\_\_

**Multiply by 12:** \_\_\_\_\_

**Divide by number of items answered:** \_\_\_\_\_ = **PC Subscale score**

**To derive a FACT-P Trial Outcome Index (TOI):**

Score range: 0-104

$$\underline{\hspace{2cm}} + \underline{\hspace{2cm}} + \underline{\hspace{2cm}} = \underline{\hspace{2cm}} = \underline{\underline{\text{FACT-P TOI}}}$$

(PWB score) (FWB score) (PCS score)

**To Derive a FACT-G total score:**

Score range: 0-108

$$\underline{\hspace{2cm}} + \underline{\hspace{2cm}} + \underline{\hspace{2cm}} + \underline{\hspace{2cm}} = \underline{\hspace{2cm}} = \underline{\underline{\text{FACT-G Total score}}}$$

(PWB score) (SWB score) (EWB score) (FWB score)

**To Derive a FACT-P total score:**

Score range: 0-156

$$\underline{\hspace{2cm}} + \underline{\hspace{2cm}} + \underline{\hspace{2cm}} + \underline{\hspace{2cm}} + \underline{\hspace{2cm}} = \underline{\hspace{2cm}} = \underline{\underline{\text{FACT-}}}$$

**P Total score**

(PWB score) (SWB score) (EWB score) (FWB score) (PCS score)

\*For guidelines on handling missing data and scoring options, please refer to the Administration and Scoring Guidelines in the manual or on-line at [www.facit.org](http://www.facit.org).

## 9.4 EORTC-QLQ-PR25 questionnaire and scoring information

ENGLISH

### EORTC QLQ - PR25

Patients sometimes report that they have the following symptoms or problems. Please indicate the extent to which you have experienced these symptoms or problems during the past week. Please answer by circling the number that best applies to you.

During the past week	Not at all	A little	Quite a bit	Very much
31. Have you had to urinate frequently during the day?	1	2	3	4
32. Have you had to urinate frequently at night?	1	2	3	4
33. When you felt the urge to pass urine, did you have to hurry to get to the toilet?	1	2	3	4
34. Was it difficult for you to get enough sleep, because you needed to get up frequently at night to urinate?	1	2	3	4
35. Have you had difficulty going out of the house because you needed to be close to a toilet?	1	2	3	4
36. Have you had any unintentional release (leakage) of urine?	1	2	3	4
37. Did you have pain when you urinated?	1	2	3	4
38. Answer this question only if you wear an incontinence aid. Has wearing an incontinence aid been a problem for you?	1	2	3	4
39. Have your daily activities been limited by your urinary problems?	1	2	3	4
40. Have your daily activities been limited by your bowel problems?	1	2	3	4
41. Have you had any unintentional release (leakage) of stools?	1	2	3	4
42. Have you had blood in your stools?	1	2	3	4
43. Did you have a bloated feeling in your abdomen?	1	2	3	4
44. Did you have hot flushes?	1	2	3	4
45. Have you had sore or enlarged nipples or breasts?	1	2	3	4
46. Have you had swelling in your legs or ankles?	1	2	3	4

Please go to the next page

ENGLISH

During the last 4 weeks...	Not at all	A little	Quite a bit	Very much
47. Has weight loss been a problem for you?	1	2	3	4
48. Has weight gain been a problem for you?	1	2	3	4
49. Have you felt less masculine as a result of your illness or treatment?	1	2	3	4
50. To what extent were you interested in sex?	1	2	3	4
51. To what extent were you sexually active (with or without intercourse)?	1	2	3	4

PLEASE ANSWER THE NEXT FOUR QUESTIONS ONLY IF YOU HAVE BEEN SEXUALLY ACTIVE OVER THE LAST 4 WEEKS

52. To what extent was sex enjoyable for you?	1	2	3	4
53. Did you have difficulty getting or maintaining an erection?	1	2	3	4
54. Did you have ejaculation problems (eg dry ejaculation)?	1	2	3	4
55. Have you felt uncomfortable about being sexually intimate?	1	2	3	4

Questions are re-numbered from 1 to 25.

**Scoring**

	Scale name	Number of items	Item range	QLQ-PR25 item numbers
Functional scales				
Sexual activity	PRSAC	2	3	20,21
Sexual functioning	PRSFU	4	3	22 – 25
Symptom scales				
Urinary symptoms	PRURI	8	3	1 – 7,9
Bowel symptoms	PRBOW	4	3	10 – 13
Hormonal treatment-related symptoms	PRHTR	6	3	14 – 19
Incontinence aid	PRAID	1	3	8

Item range is the difference between the possible maximum and the minimum response to individual items. Values from 1 to 4 gives range=3.

**Remarks**

- Items 20 and 21 can be completed by all patients
- Items 22-25 are conditional on being sexually active, and thus will only be completed by a subgroup of patients. This will require reversing the response categories of questions 23-25 but not of 22.

For all scales, the *RawScore*, *RS*, is the mean of the component items:

$$RawScore = RS = (I1 + I2 + \dots + In) / n$$

Then for **Functional scales**:

$$Score = 1 - ((RS - 1) / range) \times 100$$

and for **Symptom scales / items**:

$$Score = \{(RS - 1) / range\} \times 100$$

Missing items are simply ignored when making the calculations for scores, the above equations for multi-item scales can be used whenever at least half of the items are completed.

All of the scales and single-item measures range in score from 0 to 100. A high scale score represents a higher response level.

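### The SAP's EORTC-QLQ-PR25 functional-scale formula gives scores from 1 down to -99, and with the bracket restored it still runs both sexual scales against the SAP's own direction rule

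*SAP*

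**What the plan says.** The Scoring table in Section 9.4 of SAP v4.2 lists two functional scales: sexual activity (PRSAC, items 20 and 21) and sexual functioning (PRSFU, items 22 to 25). The other four scales are symptom scales. The item range is given as "Values from 1 to 4 gives range=3".

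The Remarks under that table then set these rules:

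- The raw score, RS, "is the mean of the component items".
- For sexual functioning: "This will require reversing the response categories of questions 23-25 but not of 22".
- For functional scales: "Score = 1 - ((RS - 1) / range", closed and followed by multiplication by 100. As printed, the 100 multiplies the fraction and not the leading 1.
- For symptom scales: {(RS - 1)/range} x 100, with the whole fraction in braces.
- On range: "All of the scales and single-item measures range in score from 0 to 100".
- On direction: "A high scale score represents a higher response level".

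Items 20 to 25 are numbers 50 to 55 on the printed questionnaire. Items 20 and 21 ask about interest in sex and sexual activity, and item 22 asks "To what extent was sex enjoyable for you". All three run from 1 (not at all) to 4 (very much). Items 23 to 25 ask about difficulties.

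Section 6.2.3.9, under PRO analyses, plans descriptive statistics for each subscale of this questionnaire, by treatment group, at each assessment and as change from baseline.

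**The concern.** The functional formula conflicts with two other statements in the same remarks. It does not produce scores from 0 to 100, and it falls as the response rises although the text says that a high score means a higher response level.

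The two faults differ in how easily they would be noticed. Negative scores would fail any range check. If a programmer silently restores the bracket, the scores fall between 0 and 100 and look normal, but a loss of sexual activity or function appears as a rise. A reader of the by-arm tables who relies on the SAP's direction rule would then read the arm difference with the wrong sign.

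**Working it through.** **Inputs.** Item responses run from 1 to 4, so the range is 3 (Section 9.4, Scoring). RS is the item mean and also runs from 1 to 4 (Section 9.4, Remarks). Items 23-25 are recoded as 5 - x, and items 20, 21 and 22 are left alone.

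**Step 1: the three formulas over RS.**

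| RS | As printed: 1 - ((RS - 1)/3) x 100 | Bracket restored: {1 - (RS - 1)/3} x 100 | Symptom form: {(RS - 1)/3} x 100 |
|---|---|---|---|
| 1 | 1 - 0 = 1 | 100 | 0 |
| 2 | 1 - 33.3 = -32.3 | 66.7 | 33.3 |
| 3 | 1 - 66.7 = -65.7 | 33.3 | 66.7 |
| 4 | 1 - 100 = -99 | 0 | 100 |

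The stated range of 0 to 100 is not reproduced by the printed formula. The other two both reproduce it, but only the symptom form rises with RS.

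**Step 2: sexual activity (items 20, 21).** No recoding applies.

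- Not at all on both items: RS = 1. Printed 1; bracketed 100; symptom form 0.
- Very much on both items: RS = 4. Printed -99; bracketed 0; symptom form 100.

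The direction rule requires the second pattern to score higher. Only the symptom form does this.

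**Step 3: sexual functioning (items 22-25), with the SAP's recoding.**

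- Best pattern: enjoyment 4 and each difficulty item 1, that is (4,1,1,1). After recoding it is (4,4,4,4), so RS = 4. Printed -99; bracketed 0; symptom form 100.
- Worst pattern: (1,4,4,4). After recoding it is (1,1,1,1), so RS = 1. Printed 1; bracketed 100; symptom form 0.

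After recoding, a high RS already means better function on all four items. The leading 1 minus then turns the scale round again, so the item reversal and the formula reversal work against each other. Evaluating all 16 activity patterns and all 256 functioning patterns confirms that these are the extremes.

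**Step 4: other recodings of sexual functioning, bracketed formula.**

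- No recoding: the best pattern has RS = (4 + 1 + 1 + 1)/4 = 1.75 and scores (1 - 0.75/3) x 100 = 75. The worst has RS = 3.25 and scores (1 - 2.25/3) x 100 = 25. The direction is right, but the ends of the scale go to mixed patterns: (1,1,1,1) scores 100 and (4,4,4,4) scores 0.
- Item 22 alone recoded: best 100, worst 0. This works, but it is the opposite of what the SAP prescribes.

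**Step 5: effect on differences.** The printed and bracketed forms both have slope -100/3 = -33.3 per RS point; the symptom form has +33.3. Arm differences and changes from baseline therefore keep their size and change sign. Absolute scores under the printed form lie 100 - 1 = 99 points below the bracketed form.

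**The case against.** **The missing bracket may be an artefact.** The formula is display mathematics read from a PDF by a program, and a sensible programmer would restore the bracket on seeing negative scores. This stands as a caveat on the 1 to -99 result. The inner double parentheses and the braces of the next formula survived intact, which makes a lost bracket less likely but does not exclude it. The direction conflict does not depend on it.

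**The functional formula might itself be the reversal of items 23-25, with item 22 exempted.** On that reading sexual functioning would have no conflict. It does not work: the formula acts on RS, the mean of all four items, so it cannot reverse three of them and spare the fourth. Applied without item recoding, it gives the 75 and 25 of Step 4. In any case, sexual activity has no reversal instruction, and there the contradiction is plain.

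**The documents do not show which element is wrong.** The fault could lie in the formula, the reversal note or the direction sentence. This is fair. The SAP shows that they cannot all hold; the scoring manual must settle which one gives way.

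**The impact is small and recoverable.** This stands. The improvement and time-to-worsening analyses (Sections 6.2.3.9.3 and 6.2.3.9.4), and the AUC and mixed-model analyses of this questionnaire, name the urinary symptom score, whose formula is correct. The sexual scales are not among the endpoints in protocol Section 7.7.3, and sexual functioning is answered only by sexually active patients. Every variant is a linear transform of RS, so scores can be recomputed from stored responses.

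**Conclusion.** The scoring rule is wrong as written. Taken literally, it returns 1 to -99 on scales that the SAP puts on 0 to 100; this part assumes that the extracted formula matches the page. With the bracket restored, both sexual scales run against the SAP's direction rule; this part rests only on the item wording, the SAP's own recoding of items 23-25 and the definition of RS as a mean.

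The consequence is minor. Two of six subscales carry the wrong sign, and under the literal formula the wrong level, in descriptive tables by arm. No primary or secondary endpoint, significance test, alpha allocation or power figure changes.

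**What to change.** In Section 9.4, with items 23-25 reversed and item 22 not, score both functional scales as {(RS - 1)/range} x 100. This satisfies the stated range and direction together, with 0 for the least activity or worst function and 100 for the most or best. An equivalent alternative is to keep {1 - (RS - 1)/range} x 100 with the outer bracket written in, and change the recoding so that items 20, 21 and 22 are reversed and 23-25 are not. Either choice should be confirmed against the instrument's scoring manual, and the SAP should say in words what a high score means on each of the two scales.

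The cost is one formula in an appendix, plus the reversal note under the alternative. SAP v4.2 dates from September 2018, and Supplement 7 plans no further efficacy analyses. The practical step is therefore to check the derived variables for these two scales and the tables built on them. If they are wrong, recompute them from the stored item responses and footnote the direction.
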